The facilitator will monitor participants' reactions, contributions and emotional state throughout the group. The clinician will facilitate a sensitive and validating environment if a participant experiences a low level of distress during the group. If required, the facilitator will sensitively raise any concerns about emotional wellbeing with the participant after the group in private and attempt to resolve this in collaboration with the participant. If appropriate, consent will be sought to inform their midwife of their distress. If a participant leaves the online meeting in distress, the facilitator will attempt to contact them after the group to debrief. A more senior member of the research team will be available for supervision during the times that Baby CHAT is running. See Appendix 3 for the distress pathway.

Participants will be able to contact the research team following the group for a debrief. All participants will be signposted to further information and support, including their general practitioner, midwife, local psychological therapies service, and other online resources. Information on participants' experiences of the intervention will be collected via the feedback form to support detection of adverse events.

If there is a potential safeguarding concern at any point during the study and the research team believes there may be imminent risk to the participant or another person, appropriate action will be taken (see Appendix 4 for the study safeguarding pathway). Safeguarding issues may arise during the main group, for example, if a participant mentions something concerning about themselves, their unborn baby or someone else. If this occurs, a facilitator will attempt to contact the participant after the group to gain further information and remind them of the limits of confidentiality. Risk concerns will be escalated to an appropriate member of the research team or the participant's clinical team if applicable. Some participants will already be under the care of a mental health team, while some pregnant women with a history of mental health problems may be well-known to their midwife and have more frequent contacts with the midwifery team throughout their pregnancy. If there is felt to be an imminent and serious risk to the participant or someone else, crisis or emergency services will be contacted.

Screening procedure

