No significant changes will be made to the Baby CHAT group content for the purposes of this study. Baby CHAT was designed as a standalone session, that could be used as an add-on to existing treatments, and therefore does not target symptoms of depression specifically. However, the nature of the group discussions may naturally differ given that all participants will be experiencing depression during their pregnancy. Group facilitators will present the Baby CHAT content in a sensitive and non-blaming manner, validating participants' experiences. The facilitators will also sensitively facilitate discussions during the group around the group content, for example, anticipated difficulties engaging in new activities while experiencing depression.

While Baby CHAT was originally designed to be delivered face-to-face, in this study all sessions will be held virtually using video conferencing software. This will facilitate participants' access to the group and enable greater safety relating to the risk of Covid-19. Groups will be offered at a mixture of times, including weekdays and evenings.

End of study definition

The study will be considered completed once participants of the last Baby CHAT group have completed 1-month follow-up questionnaires. The REC will be informed once the study has ended.

6. Assessment of Safety

Adverse event reporting will take place following the intervention via the Baby CHAT feedback form. Participants will be asked if they experienced any negative effects from attending the group. These will be recorded and reported in the Annual Progress Report and copied to the sponsor.

SAEs are defined in this study as any adverse event which: results in death; is life-threatening; requires hospitalisation or prolongation of existing hospitalisation; results in persistent or significant disability or incapacity; or consists of a congenital anomaly or birth defect. SAEs are not anticipated to occur due to any of the study procedures. However, it is expected that SAEs may occur during the study for other reasons. Hospitalisation, likely due to complications with participants' pregnancies, will be considered an unrelated but expected SAE. Where SAEs are made known to the research team, these will be documented. Suspected unexpected serious adverse reactions (SUSARs) will be reported to the REC within 15 days of the Chief Investigator becoming aware.

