Appendix 4 – Safeguarding pathway

Appendix 5 – Feedback Form

Participant ID:

Baby CHAT Group Feedback

Thank you for coming to Baby CHAT.

We would really like your feedback on Baby CHAT. Please let us know anything that you enjoyed as well as anything you think we could do to improve Baby CHAT.

Your feedback will add to our Baby CHAT research. We would like to include your feedback in our report about Baby CHAT. When we do this, we make sure that the feedback is completely anonymous so no one will know who has written the comments.

Date you attended Baby CHAT:

1. Did you think the timing of the group in your pregnancy was (please circle):

Too early

About right

Too late

Please explain your answer:

.....
.....
.....
.....

2. Was the length of the group (please circle):

Too long

About right

Too short

Please explain your answer:

.....
.....
.....
.....

3. What did you enjoy about the group?

.....
.....
.....
.....

4. What information did you find most useful from the group? Why?

.....
.....
.....
.....

5. Is there anything we can do to improve Baby CHAT?

.....
.....
.....
.....

6. Was the group relevant to people with low mood? Why/why not?

.....
.....
.....
.....

7. What did you think about the 4D scan video footage? Did this give you any ideas about how your own baby is developing?

.....
.....
.....
.....

8. Do you have any other comments or feedback on the group?

.....
.....
.....
.....

Thank you for taking the time to complete this questionnaire.

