Appendix 6 – Feedback Form – Follow-Up

Participant ID:

Baby CHAT Group Feedback – Follow-Up

We would really like your feedback on whether Baby CHAT has been helpful over the weeks since you attended. Please let us know anything that you have noticed or remembered over the last few weeks.

Your feedback will add to our Baby CHAT research. We would like to include your feedback in our report about Baby CHAT. When we do this, we make sure that the feedback is completely anonymous so no one will know who has written the comments.

Date you attended Baby CHAT:

1. How much have you thought about Baby CHAT since attending (please circle):

A lot

Sometimes

Rarely/never

Please explain your answer:

.....
.....
.....

2. What have been the lasting impacts of Baby CHAT, if any:

.....
.....
.....

3. Do you think attending Baby CHAT has helped your mood? Why/why not?

.....
.....
.....

4. Do you have any other comments or suggestions about the impact of Baby CHAT over time? Is there anything else that might be helpful?

.....
.....
.....

Thank you for taking the time to complete this questionnaire.

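### Section 6 relies on the feedback form to ask every participant about negative effects, but no item on either appended form asks

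*Combined protocol and SAP*

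**What the plan says.** Section 6 (Assessment of Safety) names the instrument: "Adverse event reporting will take place following the intervention via the Baby CHAT feedback form". The next sentence gives the content: "Participants will be asked if they experienced any negative effects from attending the group". The one after gives the destination: "These will be recorded and reported in the Annual Progress Report and copied to the sponsor".

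Section 4 (Risks/burdens) gives the form a similar role in weaker words: information on women's experiences "will be collected via the feedback form to support detection of adverse events". The flowchart in Section 2.3 marks adverse events once, after the intervention, in the same column as the feedback form.

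The forms themselves are in Appendices 5 and 6. Appendix 5 opens with a general request for feedback and then specifies: "Please let us know anything that you enjoyed as well as anything you think we could do to improve Baby CHAT". It closes with a catch-all: "8. Do you have any other comments or feedback on the group". The nearest items on Appendix 6 are "2. What have been the lasting impacts of Baby CHAT, if any" and "3. Do you think attending Baby CHAT has helped your mood? Why/why not".

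**The concern.** The protocol promises a direct question to participants and names the form that will carry it, but the form as appended does not contain that question.

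This matters because Section 4 (Risks/burdens) anticipates a specific kind of harm: guilt about current behaviour or an earlier pregnancy, and distressing thoughts about not bonding. It says such reactions are more likely in this group than in the general population. Section 2.2 adds that, to the authors' knowledge, Baby CHAT has not been trialled before in pregnant women with depression. Reactions of this kind may be private, and a woman may not volunteer them when asked what she enjoyed or what could be improved. The answers feed the annual report and the sponsor, and would inform any larger trial. A count of self-reported harms has little meaning if the question was not put.

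**Working it through.** No sample-size or error-rate formula applies. The check is an item-by-item reading of the two forms against Section 6.

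**1. Are the forms complete as printed?** Section 4 (Baby CHAT Feedback Form) describes a post-group form of 8 open-ended items, 2 with a closed part, and a follow-up form of 4 open-ended items, 1 with a closed part.

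- Appendix 5: 8 items counted; closed parts on items 1 and 2, so 2. Agrees.
- Appendix 6: 4 items counted; a closed part on item 1, so 1. Agrees.

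The numbering is unbroken and each form ends with a closing line. The missing question is not explained by lost text.

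**2. Does any item ask about negative effects?**

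| Form | Item | Subject | Asks about negative effects? |
|---|---|---|---|
| App. 5 | 1 | Timing in pregnancy | No |
| App. 5 | 2 | Length | No |
| App. 5 | 3 | Enjoyment | No |
| App. 5 | 4 | Most useful information | No |
| App. 5 | 5 | Improvements | No |
| App. 5 | 6 | Relevance to low mood | No |
| App. 5 | 7 | 4D scan footage | No |
| App. 5 | 8 | Other comments | No |
| App. 6 | 1 | How much the group was thought about | No |
| App. 6 | 2 | Lasting impacts | No (neutral wording) |
| App. 6 | 3 | Whether mood was helped | No (asks about benefit) |
| App. 6 | 4 | Other comments on impact over time | No |

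Result: 0 of 8 and 0 of 4, or 0 of 12 in all. Appendix 5 item 3 asks about enjoyment and has no negative counterpart.

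**3. Does the stated purpose of the form fill the gap?** No. Section 4 gives the aim of the post-group form as developing the group for future use and does not mention safety there.

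**4. Could the EPDS stand in?** Only in part. It covers symptoms over the previous 7 days and does not ask whether the group caused them. The post-group EPDS is due within 48 hours (2 days). If it is completed on schedule, at least 7 − 2 = 5 of the 7 days recalled fall before the group (5/7 = 71%). At 1 month all 7 days fall after the group, but the weeks in between are not covered, and the EPDS still does not link symptoms to attendance.

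**The case against.** The strongest counter-argument is that Section 6 may intend a separate enquiry by the researchers. The sentence about asking participants names no instrument. The flowchart gives adverse events a row of their own, separate from the feedback form. Section 9 (Case Report Form) provides an adverse events log for each participant, completed by the co-investigators after each trial procedure. Facilitators also watch for distress, follow up concerns in private and try to contact anyone who leaves upset; women can ask for a debrief. The open items, including those on low mood and lasting impacts, could draw out a negative effect. Appendices 3 and 4 may contain figures that could not be read here.

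Much of this stands as mitigation. Events could reach the annual report by routes other than the forms, and worsened mood may well be noticed. It does not remove the mismatch. The sentence immediately before names the form as the route, and nowhere does the text say who else would ask, when or how. The log is a place to record events; it is not described as a question put to participants. Monitoring depends on visible distress in an online group of up to eight, or on the woman making contact. Appendices 3 and 4 are presented as pathways for responding to distress or safeguarding concerns. If a separate enquiry was intended, Section 6 still needs correcting.

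A form item also has a limit: it reaches only women who return the form. Section 3 accepts 70% completion of study measures. If that threshold covers the feedback form and all 24 attend, 0.70 × 24 = 16.8, so 17 completers would meet it and up to 7 women could give no answer.

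**Conclusion.** The concern holds. Section 6 and the appended forms contradict each other: a question is promised and 0 of 12 items ask it. With the forms as they stand, self-reported negative effects depend on unprompted free text, and their absence from the forms cannot be read as women having been asked and answered no.

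The conclusion assumes that the appended forms are the ones used and that no undocumented enquiry is made of every participant. The evidence about the forms is firm. The absence of any other universal question is less certain, because figures in Appendices 3 and 4 may be missing. Given the partial safeguards and the small single-session design, this should be fixed, but it does not undermine the study as a whole.

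**What to change.** Reconcile Section 6 with the form in one of two ways.

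- **Add an item to Appendix 5.** One Yes/No question on whether attending Baby CHAT had any negative effect, with space to describe it. In Section 4, the form then has 8 + 1 = 9 items, 8 + 1 = 9 open-ended questions and 2 + 1 = 3 with closed parts. Report the number who answered and the number who reported an effect. A blank Yes/No can be chased under the existing rule in Section 3 (Statistics) for missing items on forms other than the outcome questionnaires.
- **Or, if a researcher enquiry was meant,** state in Section 6 who asks, when, and where the answer is recorded, and stop naming the form as the route.

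Repeating the item at 1 month is optional and not needed to resolve the mismatch. If it is done, the flowchart should show both the follow-up form and adverse events at that visit.

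The first option costs one item on a form already collected through Qualtrics, three changed numbers and an amendment. It needs no extra staff, visit or routine contact.

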2.3 Study Flowchart

	Screening	Baseline	Intervention	Post-intervention	1-month follow-up
Written informed consent	X				
Demographics	X				
EPDS	X			X	X
MAAS		X		X	X
P-PRFQ		X		X	X
Baby CHAT intervention			X		
Feedback form				X	
Adverse events				X	

3. Sample Size, Statistics, Selection and Withdrawal of Subjects

Sample size

This study is concerned with generating descriptive statistics to assess the feasibility of the proposed methods, rather than establishing effectiveness or generalisability of the intervention. There has been disagreement in the literature on appropriate sample sizes for feasibility studies, but sample sizes between 24 and 50 have been recommended (Lancaster, Dodd & Williamson, 2004; Sim & Lewis, 2012; Julious, 2005). To further aid decision-making regarding an appropriate sample size for the current project, sample sizes of similar studies in the field were also reviewed. These included N=24 in the treatment arm for the intervention Nurture and Play (Salo et al., 2019), and N=25 for a feasibility trial of the Beating the Blues Before Birth intervention (Milgrom et al., 2015).

In qualitative studies, there is often less rigour in the choice and justification of the sample sizes used (Marshall et al., 2013). Qualitative research often concerns developing a depth of understanding, and therefore data saturation, that is, the point at which including more participants no longer contributes additional perspectives, is often suggested as a guide for ending recruitment (Glaser & Strauss, 1967). However, this provides little guidance for estimating sample sizes prior to data collection. Determination of appropriate sample sizes in advance will depend on the context and scientific paradigm of the research (Boddy, 2016). This study involves a brief qualitative component designed to generate a breadth of feedback on the intervention. Meanwhile, it is feasible to ask all participants to provide qualitative feedback, using the questionnaire following completion of the intervention.

Taken together, a sample size of N=24 is estimated as appropriate for both the quantitative and qualitative components of the study. This is expected to be achievable based on current recruitment rates in a similar study with women with prenatal depression (the DAWN trial; Trevillion et al., 2020) and given that in 2020, around 925 babies were born in Southwark, Lambeth and Lewisham each month (Office for National Statistics, 2020).

Participant selection

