Following informed consent, the depression screening measure (the EPDS) will be conducted. Participants will be informed in a timely and sensitive manner whether they have met the criteria

to be included in the study. Participants who consent but do not score above the threshold on the screening questionnaire will be signposted to appropriate sources of support (as above, see Exclusion criteria).

Study schedule

Following inclusion in the study (i.e. having completed informed consent and scored over the screening threshold), participants will be asked to complete the baseline set of outcome questionnaires via Qualtrics (Time 1). Once completed, the participant will be booked into an upcoming session of the Baby CHAT group.

Participants will attend an online Baby CHAT group at a time that is convenient for them. Up to eight women will be invited to each group, to facilitate optimal group dynamics and engagement with the group content. See below for further details of the intervention.

After attending Baby CHAT, participants will be asked to complete the post-intervention outcome questionnaires and feedback form within 48 hours of the group (Time 2). One month later, participants will be contacted to complete the final follow-up questionnaires (Time 3).

Measures

The primary clinical outcome will be prenatal bonding as measured using the Maternal Antenatal Attachment Scale (MAAS). Secondary clinical outcomes of RF and depressive symptomology will be measured using the Prenatal Parental Reflective Functioning Questionnaire (P-PRFQ) and the Edinburgh Postnatal Depression Scale (EPDS). Feedback forms, containing both qualitative and quantitative components, will also be administered after participants have attended Baby CHAT in order to gather feedback on experience of the intervention (including group format, content and perceived usefulness).

Edinburgh Postnatal Depression Scale

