The feedback questionnaire (Appendix 5) was developed as part of the initial trial on Baby CHAT with the general population (Cox et al., 2020). The form has been adapted for the purpose of this study and contains eight items, consisting of eight open-ended questions, two of which additionally have closed question components. The feedback form aims to gather participants' views on their experience of the group in order to develop it for future use, including what they liked about Baby CHAT, how helpful they found the inclusion of the 4D scan footage and anything they felt could have improved the group.

A brief, follow-up feedback form was developed for the purposes of this study's longitudinal component (Appendix 6). The form consists of four open-ended questions, one of which also contains a closed question component. The items aim to evaluate participants' experiences of the impact of the intervention over time, including anything they felt could improve the longitudinal impact and whether they have noticed any subjective changes in their mood.

Intervention

Baby CHAT is an approximately 90-minute group intervention to be delivered during pregnancy. The group is comprised of psychoeducational material about a baby's social development after birth and while the baby is growing in the womb. Attendees are encouraged to think about when an infant's social development begins and consider whether this occurs before or after birth. Participants are then shown a video clip of Reissland et al.'s (2016) study showing 4D ultrasound images of foetuses mouthing in response to sounds that are presented to them outside the womb. Reissland's research suggests that babies' social development may begin to occur as early as 32 weeks. During Baby CHAT, parents are encouraged to reflect on this information in the context of their own baby's development, including their likes and dislikes, routine and personality. The final section of the group involves generating ideas for social activities that parents can try with their baby prior to birth, such as singing to, massaging or reading to their baby. At the end, participants are asked to think about a positive take-home message from the session and, if they feel comfortable, to share this with the group. A Baby CHAT handout will be provided for participants to work through during the group and to refer to at home. See Appendix 7 for the full session plan.

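### Serious adverse events are captured only passively and no printed form asks about them, so a low or zero count cannot be read as a rate over the women enrolled.

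*Combined protocol and SAP*

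**What the plan says.** **Definition.** Section 6 (Assessment of Safety) sets the scope by seriousness and not by relatedness: "SAEs are defined in this study as any adverse event which: results in death; is life-threatening; requires hospitalisation or prolongation of existing hospitalisation". The list continues with lasting disability and congenital anomaly. The plan does not foresee SAEs caused by study procedures, but it adds: "However, it is expected that SAEs may occur during the study for other reasons". It names the likely kind: "Hospitalisation, likely due to complications with participants' pregnancies, will be considered an unrelated but expected SAE".

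**Capture of SAEs.** The rule is: "Where SAEs are made known to the research team, these will be documented". No section says who asks, when, or over what period.

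**Capture of other adverse events.** Section 6 routes these through the feedback form given after the group: "Participants will be asked if they experienced any negative effects from attending the group". Section 4 (Study schedule) makes that form due within 48 hours. In the Section 2.3 flowchart the row "Adverse events" has one mark, at post-intervention, and none at the 1-month follow-up.

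**One-month contact.** Section 4 has participants contacted again one month after the group for the Time 3 questionnaires. It also describes a short follow-up feedback form, printed as Appendix 6.

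**Records.** Section 9 (Case Report Form) gives each participant an adverse-event log and an SAE form. The Co-Investigators complete the case report form at registration and after each trial procedure.

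**The concern.** The plan expects a class of serious event and then provides no step that would find it. A woman admitted with an obstetric complication two weeks after the group has no question to answer about it. She may be in touch with the study team again only to fill in questionnaires on other subjects. A blank SAE form would then mean either that nothing happened or that nobody asked, and the record could not tell the two apart.

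Section 2.2 says that feasibility findings can inform larger trials, and Section 4 (Risks/burdens) describes the women as potentially vulnerable. A safety count carried forward from this study should come with a known number of women asked. As planned, it would not.

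**Working it through.** The documents give no SAE rate, no capture rate and no planned SAE denominator, so there is no stated figure to reproduce. The check has two parts.

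**1. Does any scheduled instrument ask about serious events?**

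- *Appendix 5 (Time 2).* Section 4 says the form has eight items, and all eight are printed. They cover timing in pregnancy, length, what was enjoyed, what was useful, improvements, relevance to low mood, the scan footage and other comments. None asks about negative effects, admissions or serious events. The question promised in Section 6 is therefore absent from the printed form.
- *Appendix 6 (Time 3).* It has four items: how often the woman has thought about the group, lasting impacts, mood, and other comments. None asks about admissions or serious events.
- *MAAS, P-PRFQ and EPDS.* As described in Section 4, these measure attachment, reflective functioning and depressive symptoms. Item 10 of the EPDS asks about thoughts of self-harm, not about events.
- *Case report form (Section 9).* The log and SAE form are completed by staff. No section says that women are questioned in order to fill them.
- *Appendix 1.* The 15-day SAE report runs from when the Chief Investigator becomes aware, so it depends on the same passive route.

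No instrument asks. The interval from consent to the group is not covered either.

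**2. What does incomplete capture do to a zero count?**

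Inputs: N = 24 (Section 3, Sample size). The capture share *s*, meaning the proportion of women with an SAE whose event becomes known to the team, is an assumption. So is the true rate *p*.

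The one-sided 95% upper limit for 0 of *n* with full capture is 1 − 0.05^(1/n). For n = 24 this is 1 − 0.05^(1/24) = 0.1173, or 11.7%. If only a share *s* is captured, recorded events occur at rate p × s, so the limit on *p* becomes 0.1173 / s. The chance of recording none is (1 − p × s)^24.

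| Capture share *s* (assumed) | Upper limit on true rate after 0 of 24 | Chance of recording none if *p* = 10% | Chance of recording none if *p* = 20% |
|---|---|---|---|
| 100% | 11.7% | 8.0% | 0.5% |
| 75% | 15.6% | 15.4% | 2.0% |
| 50% | 23.5% | 29.2% | 8.0% |
| 25% | 46.9% | 54.5% | 29.2% |

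Worked row: at s = 50%, 0.1173 / 0.5 = 0.235, and (1 − 0.10 × 0.5)^24 = 0.95^24 = 0.292.

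If every woman reached were asked, the same formula would apply to the number asked. Zero of 20 (the attendance threshold in Section 3) gives 13.9%. Zero of 17 (70% of 24 is 16.8, rounded up, from the completion threshold) gives 16.2%. These limits are wide, but they can be interpreted. The limit under the present plan cannot be stated, because *s* is unknown.

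**The case against.** The strongest reply is proportionality. The intervention is one online psychoeducational session of about 90 minutes. Section 6 says openly that SAEs are not anticipated from study procedures and classes pregnancy-related admission in advance as unrelated but expected. No objective, outcome or threshold concerns an SAE rate. This stands, and it limits the weight of the point. It does not explain why unrelated events are included in the definition and then left to chance.

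A second reply is that information can reach the team in other ways. Facilitators watch for distress, women may contact the team for a debrief, many are recruited through treating services, and both feedback forms have open comment boxes. These routes may bring some events to light. None is a systematic inquiry, and none tells the analyst how many women were asked.

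Four stronger readings are tempting, and the documents do not support them.

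- *A reader might infer that the SAE count has no denominator at all.* The numbers enrolled and attending will be known, and each participant has a case report form with an SAE form. What is unknown is the number of women asked, so the weakness is under-capture in the numerator.
- *A reader might infer that every woman is contacted at one month.* Time 3 is described as following attendance, and Section 3 says no further data are collected from women who withdraw.
- *A reader might measure the loss by the share of the follow-up month that falls after the 48-hour form.* That is a share of days, not of missed events, and it leaves out the time between consent and the group.
- *A reader might infer that the final report will claim there were no SAEs.* No section plans such a statement.

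Listing congenital anomaly in the definition also does not promise follow-up to birth. The plan should simply say that such outcomes are not ascertained. If the group follows soon after entry at 20 to 34 weeks, and one month is taken as about four weeks, Time 3 falls at about 24 to 38 weeks.

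**Conclusion.** The point holds in this form: SAE capture is passive, no printed form asks about serious events, and the one-month contact is not used to ask. A low or zero count therefore cannot be turned into a rate over the women enrolled. As an illustration, halving capture doubles the upper limit after 0 of 24 from 11.7% to 23.5%. The 11.7% reflects the small sample and needs complete capture. The 23.5% rests on the assumed 50%, for which the documents give no basis.

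The mismatch between Section 6 and Appendix 5 on the negative-effects question is a direct inconsistency and needs no assumption. It means that the one scheduled adverse-event point has no dedicated item behind it on the printed form. If the online version does carry the question, the appendix should be updated to show it.

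The consequence is modest for this study's own aims. The change is still worth making, because the plan expects these events and a suitable contact already exists.

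**What to change.** 1. Add to Appendix 5 the negative-effects question that Section 6 says it contains.
2. Add one question to the Time 3 form on any hospital admission or other serious health event since consent, recording admission for delivery separately.
3. Mark adverse events at the 1-month follow-up in the Section 2.3 flowchart. The follow-up feedback form could be added to the flowchart at the same time, since it is missing there.
4. State in Section 6 that SAEs will be reported for the period from consent to Time 3, over the number of women actually asked, with the numbers enrolled and attending alongside.
5. State that birth outcomes after Time 3 are not ascertained.

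The cost is two questions on existing forms, the flowchart marks and a few sentences. The real burden is that asking will bring in unrelated obstetric admissions, each needing an SAE form. Section 6 names only suspected unexpected serious adverse reactions for reporting to the ethics committee, while Appendix 1 lists SAEs without that limit for reporting within 15 days. The two passages must be reconciled before the Time 3 question is introduced, so that the team knows what each reported admission requires.
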